5.2.3 Safety

The investigator will evaluate subject safety by AE monitoring, physical examination, vital signs and safety laboratory tests (see [Table 2](#)).

5.2.3.1 Adverse event monitoring

All AEs occurring from the start of first study medication (Day 1) must be documented as an AE, regardless of whether the event is considered to be related to the study drug or not (see Section [7.1.1](#)).

If possible, a diagnosis should be documented rather than signs and symptoms. All AEs should be recorded in the English language. The investigator should consider whether reports from the parents, legally acceptable representatives or caregivers should be recorded as AEs.

Subjects who withdraw because of a drug-related AE should be followed up until recovery. Adverse events will be recorded throughout the study, from the start of first study medication (Day 1) to the final assessment at follow-up. Reporting of SAEs is described in Section [7.2.2](#).

5.2.3.2 Laboratory tests

Blood and urine samples obtained at screening and at the follow-up evaluation on Day 7±3 will be analysed for the following safety laboratory parameters:

Haematology:	Haematocrit, red blood cell (RBC) count, total and differential white blood cell (WBC) count, platelet count, and reticulocyte count.
Blood chemistry:	Aspartate aminotransferase (AST) alanine aminotransferase (ALT), total bilirubin, creatinine, sodium, chloride and potassium.
Urinalysis:	Dipstick for pH, glucose*, blood*, and protein.* (*Microscopic examination of sediment if positive)

The choice of site and procedure for blood draws (e.g., venous site or heel-prick, or through an existing arterial line) will be made by the investigator depending on the availability of access, the volume of blood required, and the type of laboratory test to be done. Blood draws should be performed according to standard procedures of the institution.

The anticipated volume of blood required for PK assessment will be approximately 1.2 mL to 1.8 mL (6 sampling time points, see [Table 3](#), with a blood volume of 200–300 µL per sample).

5.2.3.3 *Physical examination*

Each subject will undergo a physical examination at screening, on Day 1 and at the follow-up assessment on Day 7±3. Abnormalities will be described in the eCRF.

Physical examination and body weight obtained during the screening evaluation do not need to be repeated as Day 1 assessments if they were performed within 6 hours prior to dosing on Day 1.

5.2.3.4 *Vital signs*

Vital signs will include body temperature, respiratory rate, pulse rate, and systolic and diastolic blood pressures. Vital signs will be measured at the times described in [Table 2](#) and [Table 3](#), and results will be entered into the eCRF.

Note: Body temperature may be measured either axillary, orally, rectally, tympanic or skin temperature (e.g. by a patch); however, for each subject only one method should be used consistently throughout the entire study.

6 STUDY DRUGS

6.1 Dose and schedule

Subjects will receive a single infusion of ceftobiprole medocartil, given in a weight-adjusted volume at a constant rate over 4 hours. The dose will be 7.5 mg/kg, calculated as ceftobiprole equivalents (7.5 mg ceftobiprole corresponds to 10.0 mg ceftobiprole medocartil sodium).

Ceftobiprole must be administered via a separate infusion line. No other intravenous infusion may be given through the same line during the 4-hour ceftobiprole infusion, and – if feasible – attempts should be made to not simultaneously administer any other antibiotic treatment (i.e., through any infusion line) during the ceftobiprole infusion. If feasible, attempts should be made to allow for a minimum period of 30 minutes between the end of administration of any other antibiotic treatment and the start of ceftobiprole medocartil infusion.

As described in [Section 3.3](#), subjects will be assigned to 3 cohorts on the basis of gestational age, and further stratified by post-natal age. The 3 cohorts will be dosed sequentially. Subjects in Cohorts 2 and 3 may not be dosed until at least 5 subjects from the previous cohort have received their full planned dose and undergone the follow-up safety evaluation (Day 7±3).

Before initiation of dosing in Cohort 2 and Cohort 3, available safety data from subjects in the previous cohort will be made available to all investigators, and the decision to initiate dosing in a new cohort will be made jointly by the sponsor and the investigators.

6.2 Administration

Details on study drug preparation and administration are described in the Study Drug Administration Manual (provided separately). Sterile technique will be used in all stages of preparation. Procedures can be briefly summarized as follows:

- a) Ceftobiprole medocaryl will be supplied in vials containing 500 mg ceftobiprole (corresponding to 667 mg of ceftobiprole medocaryl) as lyophilized powder.
- b) The vial will be reconstituted with 10 mL dextrose 5% to obtain a reconstituted solution of a concentration of 50 mg/mL ceftobiprole.
- c) 4 mL (equivalent to 200 mg ceftobiprole) of this reconstituted solution will be further diluted with 46 mL of dextrose 5% in a 50 mL syringe. The final volume in the syringe will be 50 mL, and the concentration of ceftobiprole in that 50 mL syringe will be 4 mg/mL.
- d) Depending on the body weight of the subject, the required volume corresponding to a dose of 7.5 mg/kg ceftobiprole will be infused using a calibrated infusion pump device as shown in [Table 4](#). For example, for a child of 1 kg body weight, 7.5 mg ceftobiprole will be administered, corresponding to 1.88 mL of the 4 mg/mL ceftobiprole solution. The infusion rate for a 4-hour infusion is therefore 0.47 mL/h.

Table 4 Ceftobiprole administration and dose calculation by body weight

Body weight (kg)	Ceftobiprole single dose (mg)	Required volume in mL of the reconstituted ceftobiprole solution (50 mg/mL)	Required volume of dextrose 5 %	Total syringe volume	Volume of the final solution for infusion administered from the 50 mL syringe	Infusion rate (mL/h)
0.7	5.25	4 mL	46 mL	50 mL	1.31 mL	0.33
0.8	6	4 mL	46 mL	50 mL	1.50 mL	0.38
0.9	6.75	4 mL	46 mL	50 mL	1.69 mL	0.42
1	7.5	4 mL	46 mL	50 mL	1.88 mL	0.47
1.2	9	4 mL	46 mL	50 mL	2.25 mL	0.56
1.5	11.25	4 mL	46 mL	50 mL	2.81 mL	0.70
1.8	13.5	4 mL	46 mL	50 mL	3.38 mL	0.84
2	15	4 mL	46 mL	50 mL	3.75 mL	0.94
2.5	18.75	4 mL	46 mL	50 mL	4.69 mL	1.17
3	22.5	4 mL	46 mL	50 mL	5.63 mL	1.41
3.5	26.25	4 mL	46 mL	50 mL	6.56 mL	1.64
4	30	4 mL	46 mL	50 mL	7.50 mL	1.88
4.5	33.75	4 mL	46 mL	50 mL	8.44 mL	2.11
5	37.5	4 mL	46 mL	50 mL	9.38 mL	2.34
5.5	41.25	4 mL	46 mL	50 mL	10.31 mL	2.58
6	45	4 mL	46 mL	50 mL	11.25 mL	2.81
6.5	48.75	4 mL	46 mL	50 mL	12.19 mL	3.05
7	52.5	4 mL	46 mL	50 mL	13.13 mL	3.28
7.5	56.25	4 mL	46 mL	50 mL	14.06 mL	3.52
8	60	4 mL	46 mL	50 mL	15.00 mL	3.75

Body weight used for dose calculation will be obtained on Day 1 within 6 hours prior to dosing.

The reconstituted and infusion solutions must not be frozen, and must not be exposed to direct sunlight before infusion.

Only dextrose 5% is permitted for reconstitution and dilution. Once ceftobiprole in the vial has been reconstituted with 10 mL of dextrose, further dilution of the 4 mL from the reconstituted solution with 46 mL of dextrose 5% (to obtain a 50 mL syringe with a concentration of 4 mg/mL) must be completed within 1 hour.

The final solution for infusion in the 50 mL syringe is chemically and physically stable under the following conditions:

- 24 hours in a refrigerator (2–8 °C) followed by 12 hours at room temperature
- 12 hours at room temperature

The infusion therefore must be completed within these time limits. Reconstituted and infusion solutions must be prepared under sterile conditions. Unless the method of reconstitution/dilution precludes the risk of microbiological contamination, the solutions should be used immediately, rather than within the times based on chemical and physical stability.

Further details of ceftobiprole administration are described in the Study Drug Administration Manual (provided separately).

After the end of the ceftobiprole infusion, a 3-mL aliquot of the drug infusion solution will be collected for analysis of ceftobiprole concentration (see [Appendix 2](#)). The 3-mL aliquot must be frozen at below $-65\text{ }^{\circ}\text{C}$.

6.3 Blinding and randomization

This is an open-label study. Subjects will not be randomized, but will be enrolled and assigned to 3 cohorts on the basis of gestational age, and further stratified by post-natal age (see Section 3.3). Cohorts will be dosed sequentially, starting with higher gestational age (see Section 3.3). As described in Section 6.1, the decision to start dosing in Cohorts 2 and 3 will be made jointly by the sponsor and the investigators after review of safety data and PK data from at least 5 subjects in the previous cohort.

6.4 Packaging and labelling

Study drug vials will be supplied by the sponsor to the investigator. The sponsor will ensure that the study medication and certificates of analysis are available before the start of the study.

Study drug for i.v. administration will be presented as vials of sterile lyophilized ceftobiprole medocartil (BAL5788) containing the equivalent of 500 mg ceftobiprole. The lyophilisate will be stored in a refrigerator ($2\text{ }^{\circ}\text{C} - 8\text{ }^{\circ}\text{C}$).

The study drug vial labels will identify the sponsor, study number, vial contents, batch number, and expiry date.

Study drug will be kept in a secure location under adequate storage conditions. Further details on handling, preparation, and administration of i.v. ceftobiprole are provided the Study Drug Administration Manual (provided separately).

6.5 Compliance check and accountability

Compliance will be assessed by direct observation of each subject during infusion of the study medication, and by measurement of ceftobiprole concentrations in plasma and urine.

A Drug Dispensing Log must be kept current, and should contain the following information:

- the identification of the subject to whom the drug was dispensed (subject number)
- the date(s) and quantity of the drug dispensed to the subject
- the initials of the person who dispensed the drug (pharmacist)
- the initials of the person who administered the drug (nurse)

The inventory must be available for inspection by the Clinical Study Monitor. Drug supplies, including partially used or empty containers and the dispensing logs, must be returned to the Clinical Study Monitor at the end of the study.

When requested in writing by the sponsor, unused drug supplies may be destroyed by the investigator. Records must be maintained by the investigator which show the identification and quantity of each unit disposed of, the method of destruction (taking into account applicable legal requirements), and the person who destroyed the test substance. These records must be submitted to the sponsor.

7 SUBJECT SAFETY

7.1 Adverse events

7.1.1 Definition of adverse events

An AE is any adverse change from the subject's baseline (pre-therapy) medical condition which occurs during the course of a clinical study after test medication has been given, whether considered related to treatment or not. Treatment includes all study drugs administered during the course of the study. Events involving exacerbations or worsening of pre-existing illnesses should be recorded as AEs.

A treatment-emergent AE in this study is defined as any AE occurring between first administration of study drug and the follow-up visit at study Day 7±3. If the last scheduled study visit occurs later than 10 days after stopping the treatment, any AE occurring after Day 10 will be considered non-treatment-emergent unless reassigned based on a medical review conducted by the sponsor prior to database lock.

Adverse medical occurrences that appear between the provision of informed consent and first drug administration will be entered into the Medical History section of the eCRF.

If possible, a diagnosis should be documented rather than signs and symptoms. All AEs should be recorded in the English language.

Abnormal laboratory values or test results constitute AEs only if they induce clinical signs or symptoms, are considered clinically significant, or require therapy. These events are to be entered into the Adverse Events section of the eCRF under the signs, symptoms or diagnoses associated with them.

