5.1.1 Screening (Days -1 to 1)

A parent or legally acceptable representative must provide written informed consent for a subject to participate in the study before any study-specific procedures are carried out.

Informed consent must be obtained within 3 days prior to dosing on Day 1. Once written informed consent is obtained, subjects are considered enrolled in the study.

Subjects in the appropriate Cohort (see Section 3.3) for whom consent has been provided will undergo screening evaluations within 24 hours prior to ceftobiprole dosing. Screening evaluations and dosing may be performed on the same day (Day 1). Laboratory analyses required as part of the screening process which have been performed within the 48 hours prior to ceftobiprole dosing do not need to be repeated, regardless of whether they were performed before or after signing of the ICF.

Screening evaluations (see Table 2) will comprise:

- physical examination
- medical history (within 30 days prior to enrolment)
- review and recording of medication given within the previous 7 days, including systemic antibiotics to be given before and after ceftobiprole dosing
- safety laboratory tests (haematology, clinical chemistry, and urinalysis; see Section 5.2.3.2)
- review of enrolment criteria to ensure subject eligibility, including laboratory test results
- vital signs, body weight and height

Physical examination results and body weight obtained during the screening evaluation do not need to be repeated as Day 1 assessments if they were performed within 6 hours prior to dosing on Day 1.

Table 2 Schedule of assessments

	Screening Day –1 to 1	Dosing Day 1	Follow-up Day 7±3
SCREENING AND ADMINISTRATIVE PROCEDURES			
Written Informed consent ¹	X		
Inclusion/exclusion criteria	X		
Medical history	X		
Prior medications ²	X		
CEFTOBIPROLE ADMINISTRATION			
Infusion of ceftobiprole ³		X	
Collection of aliquot of infusion solution ⁴		X	
PHARMACOKINETIC PROCEDURES			
Blood sample collection ⁵		X	
Urine collection ⁶		X	
SAFETY PROCEDURES			
Vital signs ⁷	X	X	X
Physical examination	X	X*	X
Body weight and height ⁸	X	X*	X
Laboratory tests ⁹	X		X
Concomitant medication		X	X
Adverse events		<----- X ----->	

¹ Informed consent must be obtained within 3 days prior to dosing on Day 1.

² Prior medications administered within the 7 days prior to dosing will be collected.

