7.2 Serious adverse events

Any SAE occurring during the course of the study, irrespective of the treatment received by the subject, must be reported to the sponsor or designated safety representative within 24 hours of awareness of the event.

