7.2.1 Definition of serious adverse events

An SAE is any AE that at any dose:

- results in death
- is life-threatening
- requires in-patient hospitalization or prolongation of existing hospitalization
- results in persistent or significant disability/incapacity
- is a congenital anomaly/birth defect
- is a medically important event

Medical and scientific judgment should be exercised in deciding whether expedited reporting to the sponsor is appropriate in other situations, such as important medical events that may not be immediately life-threatening or result in death or hospitalization but may jeopardize the subject or may require intervention to prevent one of the outcomes listed in the definitions above. These situations should also usually be considered serious.

Examples of such events are intensive treatment in an emergency room or at home for allergic bronchospasm; blood dyscrasias or convulsions that do not result in hospitalization; or development of drug dependency or drug abuse. An unexpected AE is an AE the nature or severity of which is not consistent with the applicable product information.

Note: **Death** is considered an outcome of an AE. Whenever possible the underlying cause of death should be reported as the AE.

A **life-threatening AE** is any adverse experience that places the subject at risk of death at the time it occurred, i.e., it does not include an event that, had it occurred in a more severe form, might have caused death.

In-patient hospitalization is defined as any in-patient admission (even if less than 24 hours). For chronic or long-term in-patients, in-patient admission also includes transfer within the hospital to an acute/intensive care unit (e.g., from a medical floor to the coronary care unit, from the neurological floor to the tuberculosis unit).

Preplanned hospitalizations and elective surgery which are not due to a worsening or exacerbation of an underlying disease do not constitute an SAE.

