7.2.2 Reporting of serious adverse events

Any SAE occurring during the active treatment period or during the protocol-defined follow-up period until the last study visit, whether considered treatment-related or not, must be reported immediately to the sponsor's safety representative listed below. The last study visit in this study will be scheduled on Day 7 ± 3 after stopping the treatment. If the last scheduled study visit occurs later than on Day 7 ± 3 after stopping the treatment, SAEs must be reported until the actual (late) visit date.

Adverse event reporting will not be solicited after the last study visit:

- A serious adverse event (including those resulting in death) that occurs after this time and which is considered related to study drug, should be reported.
- For deaths which occur after the last study visit (until database lock) that are reported unsolicited (related or unrelated to study drug), the date of death will be captured in the eCRF.
- Serious events that are reported unsolicited after the last study visit that are unrelated to study drug will not be collected and will not be reported as serious adverse events.

Safety contact

PrimeVigilance Limited, [name]. Email: [contact] eFax (UK): [name] eFax (US): [contact]

The Sponsor's safety representative will submit reports for expeditable SAEs to health care authorities and Independent Ethics Committees / Institutional Review Boards (IECs/IRBs) as required by applicable laws and regulations.

The investigator must notify the local IEC/IRB of an SAE in writing in accordance with applicable laws and regulations.

The description of the SAE should be as complete as possible and allow for a medical assessment of the case. At a minimum, the SAE report must contain:

- a subject identifier
- an adverse event description
- action taken with regards to study drug
- outcome information
- the investigator's causality assessment

Such preliminary reports must be followed by detailed descriptions, which may include copies of hospital case reports, autopsy reports, and other documents if requested and applicable.

Causality should be rated by the investigator according to [Appendix 3](#) of the protocol.

A causal relationship is suspected for all AEs reported with a relationship of 'possible' or 'probable'.

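### A serious event caused by a study procedure between consent and dosing is recorded only as Medical History, with no expedited SAE route and no place in the adverse event tables

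*Protocol*

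**What the plan says.** **Protocol, start of participation.** Section 5.1.1: "Once written informed consent is obtained, subjects are considered enrolled in the study". Consent may be given up to 3 days before dosing and must come before any study-specific procedure.

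**Protocol, what counts as an adverse event.** Section 7.1.1 limits an AE to a change "which occurs during the course of a clinical study after test medication has been given". Section 5.2.3.1 agrees: "All AEs occurring from the start of first study medication (Day 1) must be documented as an AE". Section 7.2.1 builds on this: "An SAE is any AE that at any dose" meets a seriousness criterion.

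**Protocol, pre-dose occurrences.** Section 7.1.1: "Adverse medical occurrences that appear between the provision of informed consent and first drug administration will be entered into the Medical History section". The history taken at screening is described in 5.1.1 as "medical history (within 30 days prior to enrolment".

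**Protocol, SAE reporting.** Section 7.2: "Any SAE occurring during the course of the study, irrespective of the treatment received by the subject, must be reported to the sponsor", within 24 hours of awareness. Section 7.2.2 gives a narrower window: "Any SAE occurring during the active treatment period or during the protocol-defined follow-up period until the last study visit".

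**SAP.** Section 5.2.2 tabulates medical history by SOC and PT. Section 5.5 tabulates treatment-emergent adverse events. Section 3.2 restricts the Safety population to subjects who received some study drug.

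**The concern.** An infant is in the study from consent and undergoes study procedures before the infusion starts. If one of these causes serious harm, a site that follows 7.1.1 enters it on the same eCRF page as pre-existing illness. Nothing in that rule sends it to the sponsor's safety representative within 24 hours, or to the ethics committee as an SAE.

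Procedure harm is the harm a sponsor would want to hear of quickly in newborns, since the next infant will have the same procedure. At stake are prompt reporting and a visible place for the event in the safety output. The estimate of drug safety is not affected.

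**Working it through.** The documents give no event rate, so the check is to follow one hypothetical event through the rules: serious, caused by a study procedure, after consent and before the infusion.

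**1. Procedures in the interval.** Protocol 5.1.1 and Tables 2 and 3 schedule these before dosing:
- physical examination and vital signs
- screening laboratory tests, waived if results from the 48 hours before dosing exist
- urine collection from −2 to 0 h, with no catheter placed for the study
- the pre-dose PK blood sample

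**2. Size of the pre-dose PK draw.** Section 5.2.3.2 gives 1.2 to 1.8 mL for six samples of 200–300 µL. This reproduces: 6 × 0.2 = 1.2 mL and 6 × 0.3 = 1.8 mL. One sample of six is pre-dose, so 0.2–0.3 mL, or 1/6 = 17% of the PK volume. Any screening laboratory draw is additional.

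**3. Route of the event.**

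| Question | Rule | Answer |
|---|---|---|
| Is the infant in the study? | Protocol 5.1.1 | Yes, from consent |
| Is the event an AE? | Protocol 5.2.3.1, 7.1.1 | No, it precedes study drug |
| Is it an SAE? | Protocol 7.2.1 | No, an SAE is a kind of AE |
| Does 7.2.2 require a report? | Protocol 7.2.2 | No, the window starts at active treatment |
| Does 7.2 require a report? | Protocol 7.2 | Unclear: the period named is the whole study, but the term used is SAE |
| Where is it recorded? | Protocol 7.1.1 | Medical History |
| Is it in the AE tables? | SAP 5.5 | No |
| If the infant is not dosed? | SAP 3.2 | Outside the Safety population |

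**4. Cause.** Protocol 7.1.2 and Appendix 3 grade causality against study treatment only. There is no stated category for a study procedure.

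**5. Two readings, two results.** A site following 7.1.1 files the event as history. A site reading 7.2 literally reports an SAE. Screening and dosing may fall on the same day, and SAP 5.5 classifies by start date against the reference start date. If that rule is applied by date alone, a same-day pre-dose event entered as an AE would be counted as treatment-emergent.

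**6. Medical History window.** The 30-day look-back in 5.1.1 ends at enrolment, which is consent. It does not name the period from consent to dosing that 7.1.1 assigns to the same eCRF section.

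**The case against.** The strongest defence is that starting AE collection at first dose is a deliberate and coherent choice. The secondary objective is the safety of ceftobiprole, and a Safety population of dosed infants fits it. That stands, and the treatment-emergent tables need no change. It does not supply a reporting route for harm caused by the study before the drug is given.

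Several stronger readings are tempting, and the documents do not support them:

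- **That 7.1.1 and 7.2 contradict each other.** They can be reconciled: 7.2 uses the term SAE, an SAE is an AE, and an AE is post-dose. What remains is a gap in coverage and a loosely worded 7.2. The 30-day look-back can likewise be read together with 7.1.1; it simply does not name the interval.
- **That such events are never recorded or counted.** They enter the eCRF, whose data receive manual review (9.1). An eCRF opened for an infant who fails screening must still be completed (12.5.3). SAP 5.2.2 counts medical history, and worsening after dosing becomes an AE (7.1.1).
- **That the data cannot test the low-risk statement in Protocol 3.2.** That sentence concerns giving ceftobiprole, not pre-dose sampling.
- **That placing a study infusion line is a pre-dose hazard.** The separate-line rule governs the infusion. No line placement is scheduled before dosing, and adequate vascular access is an entry criterion.
- **That the gap is a large share of the risk.** With a 3-day consent interval and 6 ± 3 days of follow-up, one could compute 3/(3+9) = 25% to 3/(3+3) = 50%. This is a share of enrolled time. Screening evaluations fall within 24 hours of dosing, and time without a study procedure carries no procedure risk.
- **That the safety review meetings would not learn of the event.** They work under a charter that is not in these documents, and Protocol 6.1 speaks of available safety data, not only SAEs.

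**Conclusion.** The point holds as a coverage gap. Under the stated rules, a serious event caused by a pre-dose study procedure is recorded and tabulated only as Medical History. It has no clear expedited route and no place in the AE or SAE tables, and an undosed infant is outside the Safety population.

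The size cannot be estimated. That few events would occur is a judgement, resting on an interval of at most 3 days, few procedures and small blood volumes. The conclusion assumes that sites follow 7.1.1 as written and that no separate manual or charter supplies the missing route.

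The practical reach is also limited. SAP 2.3.1.1 reports that only Cohort 1 was completed, so new protocol wording may cover few or no further infants. The change is still worth making because it is cheap and the omission concerns harm caused by the study itself.

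**What to change.** 1. **Protocol 7.1.1, 7.2 and 7.2.2:** reconcile to one rule. From consent, a serious event that the investigator considers caused by a study procedure is reported within 24 hours, whether or not the infant is later dosed. The report form needs a place to record relation to a study procedure.
2. **Protocol 5.1.1 and 7.1.1:** keep all other pre-dose occurrences in Medical History, and word its window to run to the start of infusion.
3. **SAP 5.5:** add a listing of pre-dose procedure-related serious events, including those in undosed infants, separate from the treatment-emergent tables. Define it by time relative to the start of infusion, so that same-day events are placed correctly.

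The cost is wording in a few protocol sections, a few extra SAE forms and one listing. Correctly classified treatment-emergent counts do not change. For infants already enrolled, the listing can show only what was captured, and the documents do not say whether the Medical History page records seriousness or cause.
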